## 10.2 Describe what data will be collected.

*NOTE: For studies with multiple data collection points or long-term follow up, consider the addition of a schedule or table in your response.*

Response:

- [Each week, participants will enter the amount of time spent meditating on a form through REDCap.](#)
- [Before week 1:](#)
  - [Tinnitus Handicap Questionnaire](#)
  - [Tinnitus Handicap Inventory](#)
  - [Tinnitus Functional Index](#)
  - [Hospital Anxiety and Depression Scale](#)
  - [Mindful Attention Awareness Scale](#)
  - [University at Buffalo Tinnitus Intake Questionnaire](#)
- [After week 3:](#)
  - [Tinnitus Handicap Questionnaire](#)
  - [Tinnitus Handicap Inventory](#)
  - [Tinnitus Functional Index](#)
  - [Hospital Anxiety and Depression Scale](#)
  - [Mindful Attention Awareness Scale](#)
- [After week 8:](#)
  - [Tinnitus Handicap Questionnaire](#)
  - [Tinnitus Handicap Inventory](#)
  - [Tinnitus Functional Index](#)
  - [Hospital Anxiety and Depression Scale](#)
  - [Mindful Attention Awareness Scale](#)

 10.3 List any instruments or measurement tools used to collect data (e.g. questionnaire, interview guide, validated instrument, data collection form).

*Include copies of these documents with your submission.*

Response:

- [Tinnitus Handicap Questionnaire](#)
- [Tinnitus Handicap Inventory](#)
- [Tinnitus Functional Index](#)

- Hospital Anxiety and Depression Scale
- Mindful Attention Awareness Scale
- University at Buffalo Tinnitus Intake Questionnaire

**Commented [BF30]:** [https://drive.google.com/open?id=104a3hbqsAAkvfesLVLFQCv168M2\\_RYQa](https://drive.google.com/open?id=104a3hbqsAAkvfesLVLFQCv168M2_RYQa)

10.4 *Describe any source records that will be used to collect data about subjects (e.g. school records, electronic medical records).*

Response: No additional records will be requested or gathered from subjects.

10.5 *Indicate whether or not **individual** subject results, such as results of investigational diagnostic tests, genetic tests, or incidental findings will be shared with subjects or others (e.g., the subject's primary care physician) and if so, describe how these will be shared.*

Response: Individual subject results will not be shared with any other parties.

10.6 *Indicate whether or not **study** results will be shared with subjects or others, and if so, describe how these will be shared.*

Response: Study results will be used towards the completion of the principal investigator's Doctorate of Audiology degree, presented to the community, and published.

## 11.0 Study Timelines

11.1 *Describe the anticipated duration needed to enroll all study subjects.*

Response: Recruitment, screening and enrollment will take no more than two months.

**Commented [31]:** ATTACH Gant chart

**Commented [32R31]:** [https://docs.google.com/spreadsheets/d/14xirM\\_wiNqISiwlwV6XbiPVP1pR3fExYkp2nOtwEQ/edit?usp=sharing](https://docs.google.com/spreadsheets/d/14xirM_wiNqISiwlwV6XbiPVP1pR3fExYkp2nOtwEQ/edit?usp=sharing)

11.2 *Describe the duration of an individual subject's participation in the study. Include length of study visits, and overall study follow-up time.*

Response: Subjects will participate in the study for a total of eight weeks. After providing consent, subjects will participate in an informational session at the UB Speech Language and Hearing Clinic lasting an hour and a half. Online participants will view a video recording of this informational session before the start of the intervention.

**Commented [RJ33]:** 8 or 10 weeks?

**Commented [BF34R33]:**

This study investigates meditation practice over the course of eight weeks. The goal is averaging 30 minutes, five days each week and a requirement of at least one hour per week. Subjects can practice their meditation anywhere, on their own.

**Commented [RJ35]:** At the end of week 2 or at enrollment? This is not indicated in section 10.1.

**Commented [RJ36]:** What is the requirement? Is it 30 minutes a day for 8 weeks?

In addition to the initial information session, subjects will be asked to complete surveys that are emailed to them after the third and eighth weeks of the study and submitted through REDCap. These surveys should take less than 30 minutes to complete each time they are administered. Additionally, subjects will enter their weekly meditation times in REDCap.

11.3 *Describe the estimated duration for the investigators to complete this study (i.e. all data is collected and all analyses have been completed).*

Response: The duration to complete this study will be 10 months.

## 12.0 Setting

12.1 *Describe all facilities/sites where you will be conducting research procedures. Include a description of the security and privacy of the facilities (e.g. locked facility, limited access, privacy barriers). Facility, department, and type of room are relevant. Do not abbreviate facility names.*

*NOTE: Examples of acceptable response may be: "A classroom setting in the Department of Psychology equipped with a computer with relevant survey administration software," "The angiogram suite at Buffalo General Medical Center, a fully accredited tertiary care institution within New York State with badge access," or, "Community Center meeting hall."*

Response: The one in-person meeting of this study will be held at the UB Speech-Language and Hearing Clinic in a room equipped with a computer and projector.

12.2 *For research conducted outside of UB and its affiliates, describe:*

- *Site-specific regulations or customs affecting the research*
- *Local scientific and ethical review structure*

*NOTE: This question is referring to UB affiliated research taking place outside UB, i.e. research conducted in the community, school-based research, international research, etc. It is not referring to multi-site research. UB affiliated institutions include Kaleida Health, ECMC, and Roswell Park Cancer Institute.*

Response:

**N/A:** This study is not conducted outside of UB or its affiliates.

## 13.0 Community-Based Participatory Research

13.1 *Describe involvement of the community in the design and conduct of the research.*

*NOTE: Community-Based Participatory Research (CBPR) is a collaborative approach to research that equitably involves all partners in the research process and recognizes the unique strengths that each brings. CBPR begins with a research topic of importance to the community, has the aim of combining knowledge with action and achieving social change to improve health outcomes and eliminate health disparities.*

Response:

**N/A:** This study does not utilize CBPR.

*13.2 Describe the composition and involvement of a community advisory board.*

Response:

**N/A:** This study does not have a community advisory board.

## 14.0 Resources and Qualifications

*14.1 Describe the qualifications (e.g., education, training, experience, expertise, or certifications) of the Principal Investigator **and** staff to perform the research. When applicable describe their knowledge of the local study sites, culture, and society. Provide enough information to convince the IRB that you have qualified staff for the proposed research.*

*NOTE: If you specify a person by name, a change to that person will require prior approval by the IRB. If you specify a person by role (e.g., coordinator, research assistant, co-investigator, or pharmacist), a change to that person will not usually require prior approval by the IRB, provided that the person meets the qualifications described to fulfill their roles.*

Response: The following roles are in place for the duration of this study. All study personnel are educated, trained, and licensed as required for their delegated role in this study. All study personnel have also received the required university training.  
Principle Investigator:

- Graduate Student in Audiology
- Training and clinical experience in tinnitus management
- Participates in the Western New York Tinnitus Support Group

Study Advisor:

- Licensed Doctor of Audiology
- American Speech and Hearing Association Certified in Clinical Competence in Audiology (CCC-A)
- Training and clinical experience in tinnitus management.

**Formatted:** Font: Not Italic

**Commented [RJ37]:** This is a good start. You can always generalize qualifications (see example below).

"All study personnel are educated, trained, and licensed as required for their delegated role in this study. All study personnel have also received the required university training.

PI is an educated, trained, board certified, and licensed research professor and interventional cardiologist working at the CTRC. Sub-PIs are educated, trained, and licensed cardiac surgeons. Sub-Is are educated, trained and licensed interventional cardiologists, neurologists and echocardiographers.

Study staff will be trained in study procedures by the PI as needed."

**Formatted:** Normal (Web), Indent: Left: 0.75", Space Before: 6 pt, After: 6 pt, Outline numbered + Level: 1 + Numbering Style: Bullet + Aligned at: 0.25" + Tab after: 0.5" + Indent at: 0.5", Font Alignment: Baseline, Pattern: Clear (Custom Color(RGB(242,242,242)))

**Formatted:** Font: Italic

**Describe other resources available to conduct the research.**

14.2 *Describe the time and effort that the Principal Investigator and research staff will devote to conducting and completing the research.*

*NOTE: Examples include the percentage of Full Time Equivalents (FTE), hours per week. The question will elicit whether there are appropriate resources to conduct the research.*

**Response:** The PI will dedicate 6-12 hours weekly to this study. The PI and study advisor that are assigned to this study will be able to devote sufficient time to the procedures in adherence with the protocol.

**Commented [38]:** Again, not sure on the exact language to describe the specifics of who does what.

14.3 *Describe the availability of medical or psychological resources that subjects might need as a result of anticipated consequences of the human research, if applicable.*

*NOTE: One example includes: on-call availability of a counselor or psychologist for a study that screens subjects for depression.*

**Response:** Potential subjects scoring “abnormal” on the Hospital Anxiety and Depression Scale will be referred to area mental health services.

**Commented [RJ39]:** You can state 3 hours a week or .5 FTEs. Whatever you and your research team can devote to conducting this study (example below).

“The PI, study coordinator, or other study staff that are assigned to this study and will be able to devote sufficient time to the procedures in adherence with the protocol.”

**Commented [BF40R39]:**

14.4 *Describe your process to ensure that all persons assisting with the research are adequately informed about the protocol, the research procedures, and their duties and functions.*

**Response:** The PI will be conducting all aspects of the study. The study advisor will correspond weekly to ensure continued adherence to the protocol and procedures.

**Commented [RJ41]:** Example: “All study personnel are required to receive study specific on-site training by the study PI. The PI will discuss the protocol, the procedures, and specific duties with all study personnel before the study starts. Any training that is necessary will be done prior to start of any study procedures.”

**Commented [BF42R41]:** Since it really is just my advisor and me, it seems a little tricky to word. Is this ok?

## 15.0 Other Approvals

15.1 *Describe any approvals that will be obtained prior to commencing the research (e.g., school, external site, funding agency, laboratory, radiation safety, or biosafety).*

**Response:** Access for a location for the in-person meeting at the beginning of this study will be obtained through the study advisor.

**N/A:** This study does not require any other approvals.

**Commented [RJ43]:** Do you need approval from the area offices for recruitment?

**Commented [BF44R43]:** I'm supposing they would simply opt in or not.

## 16.0 Provisions to Protect the Privacy Interests of Subjects

16.1 *Describe how you will protect subjects' privacy interests during the course of this research.*

*NOTE: Privacy refers to an individual's right to control access to him or herself. Privacy applies to the person. Confidentiality refers to how data collected about individuals for the research will be protected by the researcher from release. Confidentiality applies to the data.*

*Examples of appropriate responses include: "participant only meets with a study coordinator in a classroom setting where no one can overhear", or "the participant is reminded that they are free to refuse to answer any questions that they do not feel comfortable answering."*

**Response:** Patients will be placed in a private location for obtaining informed consent and the administration of patient care. Participants will be informed of the group instructional meeting and requested to maintain the privacy of others during the consent process. All steps will be taken to ensure that patient's privacy will be protected.

**16.2 Indicate how the research team is permitted to access any sources of information about the subjects.**

*NOTE: Examples of appropriate responses include: school permission for review of records, consent of the subject, HIPAA waiver. This question **does apply** to records reviews.*

**Response:** Consent of the subject. Any physical documents pertaining to the study (i.e.: screening forms, consent forms, and surveys) will be held in a secure location at the University at Buffalo – South Campus, [name]. Electronic information gathered by within REDCap of this information will be maintained and shared securely within REDCap.

No electronic medical records systems will be accessed or used throughout the study.

Contact information that is drawn from the Western New York Tinnitus Support group is maintained in a secured UB Box account. This information is available to the Speech-Language and Hearing Clinic, since they assist in maintaining this list.

**Commented [RJ45]:** Please delete. This describes confidentiality, not privacy. Privacy refers to an individual's right to control access to him or herself (example below).

"Patients will be placed in a private location for obtaining informed consent and the administration of patient care. Participants will not be placed in a common area and exposed to others. This is to prevent anyone else from overhearing any conversations regarding their personal information or study information. All steps will be taken to ensure that patient's privacy will be protected."

**Formatted:** Indent: Left: 0"

## **17.0 Data Management and Analysis**

**Commented [RJ46]:** Please respond to this section.

**17.1 Describe the data analysis plan, including any statistical procedures. This section applies to both quantitative and qualitative analysis.**

**Response:** Data will be collected and secured using the REDCap System. Analysis may include the use of paired t-tests and/or ANOVA with assistance from UB's office of Clinical and Translational Science Institute.

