## 1.0 Objectives

1.1 Describe the purpose, specific aims, or objectives of this research.

Response: The purpose of this mixed methods correlational study is to investigate the effects of meditation on the level of bother in tinnitus patients in the United States. The researchers seek to understand the changes in bother as compared to the amount of time spent meditating. Data is obtained through the Insight Timer mediation application. Outcome measures will include several validated and reliable measures.

1.2 State the hypotheses to be tested, if applicable.

NOTE: A hypothesis is a specific, testable prediction about what you expect to happen in your study that corresponds with your above listed objectives.

Response: The reduction level of bother of tinnitus will correlate to the amount of time spent meditating.

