## 2.0 Scientific Endpoints

2.1 Describe the scientific endpoint(s), the main result or occurrence under study.

NOTE: Scientific endpoints are outcomes defined before the study begins to determine whether the objectives of the study have been met and to draw conclusions from the data. Include primary and secondary endpoints. Some example endpoints are: reduction of symptoms, improvement in quality of life, or survival. Your response should **not** be a date.

Response: Outcomes will be measured utilizing the Tinnitus Handicap Questionnaire, Tinnitus Functional Index, Hospital Anxiety and Depression Scale, and the University at Buffalo Tinnitus Intake Questionnaire to investigate the reduction in level of bother created by the subject's tinnitus before, during, and after the study period of 8 weeks.

Commented [2]: Are these all the measures, more, less?  
Consider The Mindful Attention Awareness Scale (MAAS) and/or The Five Facet Mindfulness Questionnaire (FFMQ)

Commented [RJ3]: 12 weeks or 8?

Commented [BF4R3]: 8

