While it can be difficult to differentiate and locate the source of a patient's tinnitus, it is thought to originate in any combination of three areas – namely peripherally from the auditory system, centrally, or from somatosensory input. Tinnitus is commonly associated with specific regions of the brain, particularly, the Dorsal Cochlear Nucleus, Central Auditory Pathway, and Auditory Cortex (Han, Lee, Kim, Lim, & Shin, 2009). Most recently, using residual inhibition,

Sedley et al. found tinnitus activity in the thalamus, and contrary to expectations, almost all of the auditory cortex and large portions of the temporal, parietal, sensorimotor, and limbic cortex (2015).

Given tinnitus is believed to cause neuroplastic changes in several areas of the brain (Han et al., 2009) and that meditation and mindfulness activities are shown to make restorative changes in those same areas while improving emotional responses, this study investigates the association between the amount of time spent and type of meditation and relief from tinnitus through reduction of bother.

McKenna et al., have found significant reduction of bother in patients with chronic tinnitus through the use of Mindfulness-Based Cognitive Therapy (MBCT), a standardized approach to tinnitus management following an eight-week MBCT program led by clinical psychologists. They rightly point out that much of the current research in non-standardized approaches, like the one proposed in this study, has been limited by small sample sizes (2018). This study looks to add to the body of research for non-standardized interventions and lead to the possibility of increased access to care for patients.

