## 20.0      Withdrawal of Subjects

**N/A:** This study is not enrolling subjects. This section does not apply.

Commented [RJ48]: Please respond to this section.

20.1 *Describe anticipated circumstances under which subjects may be withdrawn from the research without their consent.*

Response: Subjects may be withdrawn for the following reasons:

- Failure to submit mediation data in a timely manner.
- Failure to complete surveys and questionnaires in a timely manner.
- Failure to comply to participating in the intervention. Subjects practicing meditation less than one hour per week may be withdrawn from the study.

20.2 *Describe any procedures for orderly termination.*

*NOTE: Examples may include return of study drug, exit interview with clinician. Include whether additional follow up is recommended for safety reasons for physical or emotional health.*

Response: Participants will be informed of their removal from the study and asked to complete questionnaires (Tinnitus Handicap Questionnaire, Tinnitus Handicap Inventory, Tinnitus Functional Index, Hospital Anxiety and Depression Scale, Mindful Attention Awareness Scale) via the REDCap system. This intervention poses low risk from discontinuing abruptly.

20.3 *Describe procedures that will be followed when subjects withdraw from the research, including retention of already collected data, and partial withdrawal from procedures with continued data collection, as applicable.*

Response: Data already collected from subjects who withdraw will be analyzed up to the point of their last completed questionnaires.

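### The only hypothesis is that reduction in bother correlates with meditation time (1.2), but the only methods named (17.1), paired t-tests and/or ANOVA with no meditation-time factor, do not test it

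*Protocol*

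**What the plan says.** The association with meditation time appears in three places.

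- **1.1** labels the study correlational and adds: "The researchers seek to understand the changes in bother as compared to the amount of time spent meditating". The same response also carries an effect aim: "The purpose of this mixed methods correlational study is to investigate the effects of meditation on the level of bother in tinnitus patients".
- **1.2** gives the only hypothesis: "The reduction level of bother of tinnitus will correlate to the amount of time spent meditating".
- **3.1** says that "this study investigates the association between the amount of time spent and type of meditation and relief from tinnitus", so it adds type of meditation to amount.

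The endpoint in **2.1** is worded differently. Its measures are there "to investigate the reduction in level of bother" before, during and after eight weeks. **4.1** describes a non-randomized interventional study and no comparison group.

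For methods, **17.1** says: "Analysis may include the use of paired t-tests and/or ANOVA", with help from the university's clinical and translational office. It does not tie either test to an objective. **17.2** answers the power question as not applicable.

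The data that 1.2 needs are collected. Under **10.2**, each week "participants will enter the amount of time spent meditating on a form through REDCap", and the bother scales are given before week 1, after week 3 and after week 8. For withdrawals, **20.3** says: "Data already collected from subjects who withdraw will be analyzed up to the point of their last completed questionnaires".

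**The concern.** The hypothesis asks whether subjects who meditate more improve more. The named methods, applied in the ordinary way to a single group measured repeatedly, ask whether the group improves on average. Neither answer implies the other: a group can improve with no relation to minutes, or show a relation to minutes with no average change.

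The risk lies in interpretation. The result that 17.1 points to is a pre-post comparison. Without a comparison group, a mean improvement could come from natural course, regression to the mean or expectation, and it says nothing about dose. If it is significant and 1.2 is the only hypothesis on paper, it is likely to be reported as support for 1.2. A correlation chosen after the data are seen would also have no prespecified scale, dose measure or handling of withdrawals.

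**Working it through.** **No plan figure to reproduce.** The protocol states no alpha, effect size, SD or power. The one documented input is the target of 30 subjects (5.1). Everything else below is assumed: two-sided alpha 0.05, the effect sizes and the distributions of minutes.

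**1. What each named test uses.**

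| Method | Uses meditation time? | Question answered |
|---|---|---|
| Paired t-test | No | Mean change (2.1) |
| Repeated-measures ANOVA over time points | No | Mean change over time (2.1) |
| ANOVA of change by dose group | Yes, if groups are defined | Could address 1.2; no groups are defined |
| Correlation or regression on minutes | Yes | 1.2; not named |

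**2. Paired t-test.** With d = mean change / SD of change, the noncentrality is d√n. For n = 30, d = 0.5 it is 0.5 × 5.477 = 2.74 on 29 df, giving power 0.754. At d = 0.3 and 0.7 power is 0.356 and 0.959. The correlation with minutes does not enter the formula.

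**3. Simulation, n = 30, d = 0.5.** Minutes are normal or right-skewed (lognormal, log-SD 0.7). Proportion of studies significant:

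| True correlation | Paired t-test | Correlation test | ANOVA, median split of minutes |
|---|---|---|---|
| 0 | about 75-76% | 5% | about 5% |
| 0.5, normal | about 76% | 83% | 61% |
| 0.5, skewed | about 76% | 74% | 43% |

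The converse also holds: with no mean change and a correlation of 0.5, the paired t-test rejects in 5% and the correlation test in 83%.

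**4. What a dose analysis can detect.** By Fisher's z, power is approximately Φ(atanh(r)√(n−3) − 1.96). With √27 = 5.196:

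- r = 0.3: 0.3095 × 5.196 − 1.96 = −0.35, power 0.36
- r = 0.4: 0.4236 × 5.196 − 1.96 = 0.24, power 0.60
- r = 0.5: 0.5493 × 5.196 − 1.96 = 0.89, power 0.81

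The smallest r with 80% power is tanh((1.960 + 0.842)/5.196) = tanh(0.539) = 0.49. A regression adjusted for baseline (27 df, normal minutes) gives nearly the same: 0.36, 0.60 and 0.81 at partial correlations of 0.3, 0.4 and 0.5.

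**5. Handling withdrawals in that regression.** Subjects who log little time may leave early, so low dose can stand in for short follow-up. Assume that minutes have no effect, that everyone improves linearly to 0.5 SD by week 8, and that the 3 or 6 subjects with fewest minutes have their last score at week 3. Skewed minutes here have log-SD 0.5.

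- Mean minutes per week, adjusted for baseline only: false-positive rate about 5.5 to 8.7% across these settings.
- The same plus weeks of participation: about 5% throughout.
- Cost of the weeks covariate at a partial correlation of 0.5: power falls from 81% to 65% (3 early leavers) or 55% (6) with normal minutes, and from 77% to 70% or 64% with skewed minutes.

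**6. Narrowed dose range.** 10.1 and 20.1 link remaining in the study to one hour per week. If those below 60 minutes contributed no later score, the correlation among the rest would shrink to r·u/√(1 − r² + r²u²), where u is the ratio of the truncated to the full SD of minutes. Assume normal minutes with SD 50 and r = 0.5. A mean of 120 gives u = 0.83 and 0.415/0.960 = 0.43. A mean of 100 gives u = 0.76 and 0.378/0.945 = 0.40. By step 4, power at r = 0.4 is about 0.60 even if 30 subjects remained.

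**The case against.** The strongest reply is that 17.1 is an open list. It excludes nothing, assigns no test to 1.2, and an analysis plan not seen here could name a correlation. That stands to this extent: a reader might infer that the protocol rules out a correlation, or that it prescribes the wrong test for 1.2, and the text supports neither. What remains is that 17.1 asks for the statistical procedures, the protocol answers with specific ones, and those do not reach its only hypothesis.

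Second, the named tests fit stated aims: the effect aim in 1.1, the endpoint in 2.1 and the design in 4.1. This also stands. A reader might infer that paired t-tests and ANOVA are wrong for the study. They are not; the gap concerns 1.2 alone.

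Third, ANOVA across levels of minutes would address 1.2. True, but no levels are given, cut-points chosen later would be arbitrary, and grouping loses power (step 3). That loss is a matter of efficiency, not an error in the document.

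Fourth, it is true by construction that a paired t-test ignores minutes, so the simulation proves nothing new. Agreed; it only shows how readily the pre-post result would appear with no dose relation present.

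**Conclusion.** The point holds as a mismatch between the only stated hypothesis and the only named methods, and should be fixed. As 17.1 stands, 1.2 has no named test, and the result it points to is equally likely whether or not 1.2 is true (about 75% under the assumed 0.5 SD change).

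The mismatch itself follows from the text and needs no assumption. Every percentage rests on assumed effect sizes, distributions, alpha and withdrawal counts, with only the 30 subjects taken from the protocol. It does not follow that the study can confirm 1.2 once the method is named: at 30 subjects, only a partial correlation near 0.5 reaches 80% power, and that is before the weeks covariate.

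**What to change.** In 17.1, name as the analysis of 1.2:

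- **Model:** linear regression of the last available post-baseline score on mean minutes per week up to that score (continuous), adjusted for the baseline score and for weeks of participation up to that score.
- **Scale:** one bother scale chosen in advance, listed in 2.1 and given at all three time points, for example the Tinnitus Functional Index (the Tinnitus Handicap Questionnaire also qualifies).
- **Report:** slope, 95% CI, partial correlation, and the number of subjects with no post-baseline score.
- **Sensitivity:** the same model in week-8 completers, where weeks of participation no longer varies and drops out.

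This uses withdrawn subjects' data as 20.3 intends, including questionnaires requested at removal (20.2), without labelling an earlier score as week 8, which 20.3 does not say.

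Keep paired t-tests and/or ANOVA for the change endpoint in 2.1, and state that a significant pre-post change is not evidence for 1.2.

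**Cost:** wording in 17.1 and the choice of one scale; weekly minutes and scores are already collected. Downsides to state: 80% power only near a partial correlation of 0.5 without the weeks covariate and lower with it (step 5); possible further loss if withdrawal below one hour per week narrows the dose range (step 6); some withdrawn subjects may not return the final questionnaires; and meditation time is self-selected, so the slope is an association and not an effect.
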